15.3 Subject Confidentiality

The sponsor and designees affirm and uphold the principle of the subject's right to protection against invasion of privacy. Throughout this study, a subject's source data will only be linked to the sponsor's clinical study database or documentation via a unique identification number. As permitted by all applicable laws and regulations, limited

subject attributes, such as sex, age, or date of birth may be used to verify the subject and accuracy of the subject's unique identification number.

To comply with ICH Guidelines for GCP and to verify compliance with this protocol, the sponsor requires the investigator to permit its monitor or designee's monitor, representatives from any regulatory authority (e.g., Food and Drug Administration, Medicines and Healthcare products Regulatory Agency, Pharmaceuticals and Medical Devices Agency), the sponsor's designated auditors, and the appropriate IRBs to review the subject's original medical records (source data or documents), including, but not limited to, laboratory test result reports, ECG reports, admission and discharge summaries for hospital admissions occurring during a subject's study participation, and autopsy reports. Access to a subject's original medical records requires the specific authorization of the subject as part of the informed consent process (see Section 15.2).

Copies of any subject source documents that are provided to the sponsor must have certain personally identifiable information removed (i.e., subject name, address, and other identifier fields not collected on the subject's eCRF).

15.4 Publication, Disclosure, and Clinical Trial Registration Policy

15.4.1 Publication and Disclosure

The investigator is obliged to provide the sponsor with complete test results and all data derived by the investigator from the study. During the study, only the sponsor may make study information available to other study investigators, sub-investigators or to regulatory agencies, except as required by law or regulation. Except as otherwise allowable in the clinical study site agreement, any public disclosure (including publicly accessible websites) related to the protocol or study results is the sole responsibility of the sponsor.

The sponsor may publish any data and information from the study (including data and information generated by the investigator) without the consent of the investigator.

The investigator or sub-investigator needs to obtain a prior written approval from the sponsor to publish any information from the study externally such as to a professional association.

15.4.2 Clinical Trial Registration

In order to ensure that information on clinical trials reaches the public in a timely manner and to comply with applicable laws, regulations and guidance, Takeda will, at a minimum register interventional clinical trials it sponsors anywhere in the world on the publicly accessible website (ClinicalTrials.gov and Japan Pharmaceutical Information Center-Clinical Trials Information) before start of study, as defined in Takeda Policy/Standard.

15.4.3 Clinical Trial Results Disclosure

Takeda will post the results of clinical trials on publicly accessible websites, as required by Takeda Policy/Standard, applicable laws and/or regulations.

15.5 Insurance and Compensation for Injury

Each subject in the study must be insured in accordance with the regulations applicable to the site where the subject is participating. If a local underwriter is required, then the sponsor or sponsor's designee will obtain clinical study insurance against the risk of injury to clinical study subjects.

Refer to the Clinical Study Site Agreement regarding the sponsor's policy on subject compensation and treatment for injury. If the investigator or sub-investigator has questions regarding this policy, he or she should contact the sponsor or sponsor's designee.

1.0 ADMINISTRATIVE INFORMATION AND PRINCIPLES OF CLINICAL STUDIES

1.1 Contacts and Responsibilities of Study-Related Activities

See Annex 1.

2.0 STUDY SUMMARY

Name of Sponsor: Takeda Pharmaceutical Company Limited	Compound: SYR-472			
Title of Protocol: A phase 3, multicenter, randomized, double-blind, placebo-controlled, parallel-group, comparative study and a phase 3, multicenter, open-label, long-term study to evaluate the efficacy and safety of SYR-472 when orally administered at a dose of 25 mg once weekly in patients with type 2 diabetes mellitus complicated by severe renal impairment or end-stage renal failure	IND No.: Not Applicable	EudraCT No.: Not Applicable		
Study Number: SYR-472-3003	Phase: 3			
Study Design: This is a phase 3, multicenter, randomized, double-blind, placebo-controlled, parallel-group, comparative study (Treatment Period I) and a phase 3, multicenter, open-label, long-term study (Treatment Period II) to evaluate the efficacy and safety of SYR-472 when administered orally at a dose of 25 mg once weekly in patients with type 2 diabetes mellitus complicated by severe renal impairment or end-stage renal failure and with inadequate glycemic control despite diet and/or exercise therapy (if any) or despite treatment with 1 antidiabetic drug (Table 2.a) in addition to diet and/or exercise therapy (if any).				
Table 2.a Concomitant Antidiabetic Drugs Permitted in the Study				
Type	Drug Name (Nonproprietary Name or Class)			
Rapid-acting insulin secretagogues	Mitiglinide calcium hydrate, repaglinide			
α-glucosidase inhibitors	Acarbose, miglitol, voglibose			
Insulin preparations	Mixed, intermediate-acting, or long-acting soluble insulin (40 units/day or less*)			
*For change in the dosing unit of insulin preparations, see 2 (2) in Section 7.3.				
Subjects who enter the screening period after signing informed consent and are considered eligible according to the inclusion and exclusion criteria will be randomly assigned to either of the SYR-472 25 mg group or placebo group. Subjects who are assigned to the SYR-472 25 mg group in Treatment Period I will continue to be treated with SYR-472 25 mg in Treatment Period II, while those assigned to the placebo group will be switched to SYR-472 25 mg in Treatment Period II.				
In Treatment Period I, 1 SYR-472 25 mg tablet or placebo tablet will be orally administered once weekly before breakfast. In Treatment Period II, 1 SYR-472 25 mg tablet will be orally administered once weekly before breakfast.				
The study period consists of 6 weeks of screening, 52 weeks of treatment, and 2 weeks of follow-up, a total of 60 weeks. The treatment period consists of Treatment Period I (double-blind) from Week 0 to Week 12 and Treatment Period II (open-label) between Week 12 and Week 52. Subjects will visit the site at the start of the screening period (Week -6), Week -2 of the screening period, end of the screening period (Week 0), Week 2 and Week 4 of the treatment period, and at every 4 weeks until Week 52 of the treatment period, and at the end of the follow-up period (Week 54) (total of 18 visits).				
The planned sample size is 106 randomized subjects (53 per group).				
Objectives: To evaluate the efficacy and safety of SYR-472 when administered at a dose of 25 mg once weekly using placebo as a control in patients with type 2 diabetes mellitus complicated by severe renal impairment or end-stage renal failure and inadequate glycemic control despite diet and/or exercise therapy (if any) or despite treatment with 1 antidiabetic drug in addition to diet and/or exercise therapy (if any); and to evaluate the long-term safety and efficacy of SYR-472 when administered at a dose of 25 mg once weekly in patients with type 2 diabetes mellitus complicated by severe renal impairment or end-stage renal failure.				

Subject Population:

Patients with type 2 diabetes mellitus complicated by severe renal impairment or end-stage renal failure and inadequate glycemic control despite diet and/or exercise therapy (if any) or despite treatment with 1 antidiabetic drug in addition to diet and/or exercise therapy (if any)

Number of Subjects:	Number of Sites:
Randomized: 53 subjects per group, 106 in total (Changed as of 12 September 2016)	Approximately 50 sites
Dose Level:	Route of Administration:
<Treatment Period I> One SYR-472 25 mg tablet or placebo tablet will be orally administered once weekly before breakfast.	Oral
<Treatment Period II> One SYR-472 25 mg tablet will be orally administered once weekly before breakfast.	
Duration of Treatment:	Period of Evaluation:
<Treatment Period I> SYR-472 25 mg tablet or placebo tablet: 12 weeks	Screening period : 6 weeks Treatment Period I : 12 weeks Treatment Period II: 40 weeks Follow-up period : 2 weeks Total : 60 weeks
<Treatment Period II> SYR-472 25 mg tablet: 40 weeks	
Criteria for Inclusion:	
1. The subject has a diagnosis of type 2 diabetes mellitus.	
2. The subject has a fasting C-peptide value of 0.6 ng/mL or higher at the start of the screening period (Week -6) and Week -2 of the screening period.	
3. The subject has a hemoglobin value of 10.0 g/dL or higher at the start of the screening period (Week -6) and Week -2 of the screening period.	
4. The subject has an hemoglobin A1c (HbA1c) value of 7.0% or higher but less than 10.0% at Week -2 of the screening period. However, subjects on hemodialysis (patients with end-stage renal failure) with an HbA1c value of less than 7.0% at Week -2 of the screening period are permitted to be enrolled if they have a glycoalbumin value of 20% or higher.	
5. <Subjects with an HbA1c value of 7.0% or higher but less than 10.0% at Week -2 of the screening period> The subject has an HbA1c value difference between the start of the screening period (Week -6) and Week -2 of the screening period within 10.0%* of the HbA1c value at the start of the screening period (Week -6). <Subjects on hemodialysis (patients with end-stage renal failure) with an HbA1c value of less than 7.0% and glycoalbumin value of 20% or higher at Week -2 of the screening period> The subject has a glycoalbumin value difference between the start of the screening period (Week -6) and Week -2 of the screening period within 10.0%* of the glycoalbumin value at the start of the screening period (Week -6).	
6. The subject has been on a fixed diet and/or exercise therapy (if any) from at least 6 weeks prior to the start of the screening period (Week -6).	
7. The subject meets any of the following:	
• The subject has not received any antidiabetic medications (including insulin preparations) from at least 6 weeks prior to the start of the screening period (Week -6).	
• The subject is being treated with 1 oral hypoglycemic drug* starting from at least 6 weeks prior to the start of the screening period (Week -6) at a fixed dose and regimen.	

*: Any of the following medications: metformin, sulfonylurea, alpha-glucosidase inhibitor, DPP-4 inhibitor, SGLT2 inhibitor, GLP-1 receptor agonist, PPAR agonist, and other antidiabetic drugs.

voglibose

- The subject is being treated with 1 insulin preparation** from at least 6 weeks prior to the start of the screening period (Week -6) at a fixed dose and regimen (≤ 40 units/day).
**: Any of the following insulin monotherapies: mixed (rapid-acting or ultrarapid-acting insulin containing no more than 30% of volume), intermediate-acting, or long-acting soluble insulin preparations
- 8. The subject is not undergoing hemodialysis or peritoneal dialysis and has severe renal impairment (creatinine clearance [Ccr] < 30 mL/min at the start of the screening period [Week -6]), or the subject is undergoing hemodialysis and has end-stage renal failure.
- 9. In the opinion of the investigator or sub-investigator, the initiation of hemodialysis or peritoneal dialysis within 12 weeks after initiation of the study drug is not expected. (in cases where the subject is not undergoing hemodialysis or peritoneal dialysis [patients with severe renal impairment])
- 10. The subject has been undergoing hemodialysis started from at least 6 months prior to informed consent and, in the opinion of the investigator or sub-investigator, the subject is clinically stable. (in cases where the subject is undergoing hemodialysis [patient with end-stage renal failure])
- 11. The subject is male or female and is aged 20 years or older at the time of informed consent.
- 12. A female subject of childbearing potential who is sexually active with a nonsterilized male partner agrees to routinely use adequate contraception from signing of informed consent until 1 month after the end of the study.
- 13. In the opinion of the investigator or sub-investigator, the subject is capable of understanding and complying with protocol requirements.
- 14. The subject signs and dates a written, informed consent form prior to the initiation of any study procedures.

Criteria for Exclusion:

1. The subject has clinically evident hepatic impairment (e.g., AST or ALT ≥ 2.5 times the upper limit of normal or total bilirubin of ≥ 2.0 mg/dL at the start of the screening period [Week -6] or at Week -2 of the screening period).
2. The subject has any serious cardiac diseases, cerebrovascular disorders, or serious pancreatic or hematological diseases (e.g., subjects who require inpatient treatment or had been hospitalized for treatment within 24 weeks prior to the start of the screening period).
3. The subject has severe ketosis, diabetic coma or pre coma, type 1 diabetes, severe infection, or severe external injury, or is immediately before or after surgery.
4. The subject has hemoglobinopathy (sickle cell disease, thalassemia, etc.).
5. The subject experienced hypoglycemia (subjects with a blood glucose value of ≤ 70 mg/dL or hypoglycemic symptoms) within 6 weeks prior to the start of the screening period or during the screening period (at least twice per week).
6. The subject has inadequately controlled hypertension.
7. For subjects who are being treated with 1 antidiabetic agent, the subject had been treated with at least 2 antidiabetic agents on the day before 6 weeks prior to the start of the screening period (Week -6) (43 days prior to the start of the screening period).
8. The subject has malignancies.
9. The subject has a history of hypersensitivity or allergies to dipeptidyl peptidase-4 (DPP-4) inhibitors.
10. The subject has a history of gastrectomy or small intestinal resection.
11. The subject is a habitual drinker and consumes a daily average of more than 100 mL of alcohol.
12. The subject has a history of drug abuse (defined as any illicit drug use) or a history of alcohol abuse.
13. The subject is required to take excluded medications during the study period.
14. The subject has received SYR-472 in a previous clinical study.
15. The subject received any investigational products (including investigational drugs in a post-marketing clinical study) within 12 weeks prior to the start of the screening period.
16. The subject is participating in other clinical studies at the time of informed consent.

CONFIDENTIAL

17. If female, the subject is pregnant or lactating or intending to become pregnant from the time of informed consent to within 1 month after the end of the study; or intending to donate ova during such time period.
18. The subject is an immediate family member, study site employee, or is in a dependant relationship with a study site employee who is involved in conduct of this study (e.g., spouse, parent, child, sibling) or may consent under duress.
19. The subject is hospitalized during the screening period or is deemed as requiring hospitalization during the study period by the investigator or sub-investigator, unless the hospitalization is for short-term evaluations including complete health checkups or for short-term admission for shunt operation (including shunt maintenance).
20. The subject is deemed ineligible for the study for any other reason by the investigator or sub-investigator.

Criteria for Evaluation and Analyses:

1. Primary Endpoints

Efficacy: Change in HbA1c at the end of Treatment Period I from the end of the screening period (Week 0)

Safety: Adverse events (AEs)

2. Secondary Endpoints

Efficacy: HbA1c, fasting blood glucose, glycoalbumin

Safety: Vital signs, 12-lead electrocardiogram (ECG), clinical laboratory values

3. Additional Endpoints

Efficacy : Fasting C-peptide, fasting glucagon, DPP-4 activity, weight

Safety : Hypoglycemia (only for subjects using insulin preparations)

Pharmacokinetics : Plasma concentration of unchanged SYR-472 (SYR-472Z)

Statistical Considerations:

1. Efficacy Analysis

<Efficacy endpoint (primary endpoint)>

Change in HbA1c at the end of Treatment Period I from the end of the screening period (Week 0)

<Analytical methods (primary analysis)>

The following analyses will be performed in the Full Analysis Set (FAS).

The population mean change in HbA1c at the end of Treatment Period I from the end of the screening period (Week 0) will be compared between SYR-472 25 mg group and placebo group based on an analysis of covariance (ANCOVA) model for the change in HbA1c at the end of Treatment Period I from the end of the screening period (Week 0) with factors of treatment group and HbA1c at the end of the screening period (Week 0).

The same ANCOVA model will be used to calculate the least square (LS) mean and the two-sided 95% confidence interval (CI) for each treatment group, as well as the intergroup difference in the LS mean between the treatment groups (SYR-472 25 mg group - placebo group) and the two-sided 95% CI.

2. Safety Analysis

<Safety endpoint (primary endpoint)>

AEs

<Analytical methods>

The following analyses will be performed in the Safety Analysis Set.

The following analyses will be performed for TEAEs that occur prior to the start of the study drug for Treatment Period II by treatment group, and for those that occur after the start of SYR-472 25 mg tablet. In the analysis of TEAEs occurring after the start of SYR-472 25 mg tablet, subjects who received SYR-472 25 mg tablet will be included in the analyses.

TEAEs will be coded using MedDRA dictionary. Frequency distributions will be provided using System

Organ Class and Preferred Term for each treatment group as follows:

- All TEAEs
- Drug-related TEAEs
- Intensity of TEAEs
- Intensity of drug-related TEAEs
- TEAEs leading to study drug discontinuation
- Serious TEAEs
- TEAEs over time

Sample Size Justification:

In Study CCT-002, the intergroup difference (two-sided 95% CI) in the mean change in HbA1c (JDS value) at the end of the treatment period (value at the end of the treatment period - value at the end of the screening period) between the SYR-472 100 mg group and placebo group was -0.56 ([-0.753, -0.367])%. In the same study, the standard deviation of the change in HbA1c (JDS value) at the end of the treatment period (value at the end of the treatment period - value at the end of the screening period) for each treatment group ranged from 0.523% to 0.628%.

In this study, which will administer SYR-472 at a dose of 25 mg once weekly to patients with type 2 diabetes mellitus complicated by severe renal impairment or end-stage renal failure, the intergroup difference in the mean change in HbA1c at the end of Treatment Period I from the end of the screening period (Week 0) between the SYR-472 25 mg group and placebo group is assumed to be -0.40%, given that the efficacy of SYR-472 25 mg in this study is similar to that of SYR-472 100 mg administered once weekly to patients with type 2 diabetes mellitus not complicated by renal impairment. The common standard deviation in each treatment group is assumed to be 0.80%.

Based on these assumptions, 86 subjects per group will be required to provide a 90% power in a two-sample t-test with a significance level of 5% (two-sided). Therefore, the sample size was set at 90 as randomized subjects per group at the start of the study allowing for the possibility that there exists some subjects whose primary endpoint cannot be evaluated.

However, achievement of the sample size as originally planned at the start of the study was found difficult because there were more than expected numbers of candidate subjects who did not provide consent and who dropped out during screening after providing consent for the study. It was therefore decided to change some of the inclusion and exclusion criteria for this study. After these changes, the ultimate number of subjects randomized and evaluable for the primary endpoints are expected to be around 53 and 51, respectively, per group.

Assuming the number of subjects per group as 51 under these assumptions, the study will provide a 70.6% power in a two-sample t-test with a significance level of 5% (two-sided).

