2.1 Primary Endpoints and Analysis Methodology

2.1.1 Primary Analysis

Analysis set: Full analysis set

Analysis variables: Change in HbA1c at the end of Treatment Period I from Week 0

Analysis methodology: The population mean change in HbA1c at the end of Treatment Period I from Week 0 will be compared between the SYR-472 25 mg/SYR-472 25 mg group and placebo/SYR-472 25 mg group based on an analysis of covariance (ANCOVA) model for the change in HbA1c at the end of Treatment Period I from Week 0 with factors of treatment group and HbA1c at Week 0. The same ANCOVA model will be used to calculate the least square (LS) mean and the two-sided 95% confidence interval (CI) for each treatment group, as well as the intergroup difference in the LS mean between the treatment groups (SYR-472 25 mg/SYR-472 25 mg group – placebo/SYR-472 25 mg group) and the two-sided 95% CI.

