2.2 Secondary Endpoints and Analysis Methodology

2.2.1 HbA1c, Fasting Blood Glucose, Glycoalbumin

Analysis set:	Full analysis set
Analysis variables:	HbA1c Fasting blood glucose Glycoalbumin
Visits:	HbA1c Weeks -6, -2, 0, 2, 4, 8, 12, 16, 20, 24, 28, 32, 36, 40, 44, 48, 52, at the end of Treatment Period I, and at the end of Treatment Period II Fasting blood glucose Weeks -6, 0, 2, 4, 8, 12, 16, 20, 24, 28, 32, 36, 40, 44, 48, 52, 54, at the end of Treatment Period I, and at the end of Treatment Period II Glycoalbumin Weeks -6, -2, 0, 2, 4, 8, 12, 16, 20, 24, 28, 32, 36, 40, 44, 48, 52, 54, at the end of Treatment Period I, and at the end of Treatment Period II
Analysis methodology:	
The following analyses (1) and (2) will be performed for the above analysis variables. Also, the following analysis (3) will be performed for HbA1c.
 
For the mean and standard deviation plot, a plot until Treatment Period I and a plot for the entire study will be created, respectively, but the plot for the entire period will not be output at Week 54 or at the end of Treatment Period I.
 
(1) Summary statistics and the two-sided 95% CI for the mean will be calculated for each visit and the mean and standard deviation plot by treatment group will be prepared. Also, the intergroup difference in the mean between treatment groups (SYR-472 25 mg/SYR-472 25 mg group – placebo/SYR-472 25 mg group) and the two-sided 95% CI will be calculated for each visit during the Screening and Treatment Period I.
 
(2) The same analysis as the above (1) will be performed for changes from Week 0 at each visit after Treatment Period I.
 
(3) For the proportions of subjects who achieved an HbA1c less than 6.0%, 7.0%, or 8.0% at the end of Treatment Period I and Treatment Period II, the proportions and the two-sided 95%

CIs will be calculated for each treatment group, and the intergroup difference in the proportions between treatment groups (SYR-472 25 mg/SYR-472 25 mg group – placebo/SYR-472 25 mg group) and the two-sided 95% CIs will be calculated at the end of Treatment Period I. In the analysis of each proportion, subjects who did not achieve the relevant target HbA1c at Week 0 will be included in the analysis.

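### The primary ANCOVA adjusts for Week 0 HbA1c only; adding the Week -6 and Week -2 values, already collected before randomisation, could improve precision at almost no cost

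*Protocol*

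**What the plan says.** The primary analysis is an ANCOVA of the change in HbA1c from Week 0 to the end of Treatment Period I in the full analysis set. Protocol Section 2.0 and Section 13.1.3 fit it "with factors of treatment group and HbA1c at the end of the screening period (Week 0" value; SAP 2.1.1 fits it "with factors of treatment group and HbA1c at Week 0". The three places agree.

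HbA1c is a central-laboratory measurement (protocol 9.1.14). SAP 2.2.1 lists the visits as "HbA1c Weeks -6, -2, 0, 2, 4, 8, 12" and onward, and the SAP time-window table gives Weeks -6, -2 and 0 separate windows. Inclusion criterion 4 (protocol 7.1) uses the Week -2 value in every subject. Criterion 5 needs both Week -6 and Week -2 in subjects who enter on HbA1c of 7.0% to under 10.0%. Haemodialysis subjects who enter below 7.0% are judged for stability on glycoalbumin instead.

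Protocol 13.1.3 also has a supplementary covariate-adjusted ANCOVA, with the further covariates to be picked when the blinded data are reviewed. It names none. SAP 2.4.1, on covariate adjustment, only refers back to 2.1.1.

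On size, the protocol first found that "86 subjects per group will be required to provide a 90% power". After the cut to 53 randomised and 51 evaluable per group, it says "the study will provide a 70.6% power in a two-sample t-test with a significance level of 5% (two-sided".

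**The concern.** Background diet, exercise and antidiabetic treatment are meant to stay fixed from 6 weeks before Week -6 to the end of Treatment Period I (protocol 6.2). The Week -6 and Week -2 readings are therefore repeat pre-dose measurements of the outcome under stable conditions. If a single HbA1c reading carries error, earlier readings help to predict the end-of-period value beyond what Week 0 alone can do. The protocol gives a reason to expect such error here: its justification of the inclusion criteria says that low haemoglobin, and in haemodialysis patients immature erythrocytes and shorter red-cell survival, can affect HbA1c.

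At stake is the width of the confidence interval for the primary difference, in a trial whose size was reduced because subjects were hard to recruit. The two readings serve eligibility and descriptive summaries, and then play no part in the treatment comparison.

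**Working it through.** **Inputs from the documents** (protocol 2.0 and 13.3): "between the SYR-472 25 mg group and placebo group is assumed to be -0.40"%; "The common standard deviation in each treatment group is assumed to be 0.80"%; 51 evaluable per group; two-sided 5%. Between-visit correlations are not given and are assumed below.

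**Reproducing the plan's figures.** For a two-sample t-test, the noncentrality is 0.40 / (0.80 × √(2/51)) = 2.525 on 100 df, which gives power 70.56%, against 70.6% stated. With 86 per group power is 90.3% and with 85 it is 89.99%, so 86 is right. Both figures are for an unadjusted test on change.

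**Method.** Hold the SD of change at 0.80. Take the covariance of HbA1c at Weeks -6, -2, 0 and 12, derive the residual SD given the covariates, and compute noncentral-t power. Error df are 99 with Week 0 alone and 98 with Week 0 plus the mean of Weeks -6 and -2.

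**(i) Equal correlation ρ between all visits.** Residual variance is 0.64(1+ρ)/2 with Week 0 only, and 0.64(1+3ρ)/[2(1+2ρ)] with the earlier mean added.

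| ρ | Residual SD, Week 0 only | Power | Residual SD, with earlier mean | Power |
|---|---|---|---|---|
| 0.5 | √0.480 = 0.693 | 82.3% | √0.400 = 0.632 | 88.5% |
| 0.7 | √0.544 = 0.738 | 77.4% | √0.413 = 0.643 | 87.5% |
| 0.8 | √0.576 = 0.759 | 75.0% | √0.418 = 0.647 | 87.1% |

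The gain is 6 to 12 points; residual variance falls by 17% to 27%.

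**(ii) The same, allowing for eligibility.** Criteria 4 and 5 narrow the spread of the earlier values. As an illustration, I simulated normal values with mean 7.6%, keeping subjects with Week -2 in 7.0% to under 10.0% and a Week -6 to Week -2 difference within 10%, with the SD of change again scaled to 0.80. For ρ = 0.5, 0.7 and 0.8, power goes from 84.1% to 88.5%, 80.4% to 87.5%, and 78.7% to 87.1%. With mean 8.0% and ρ = 0.8 it goes from 78.3% to 86.9%. The gain is about 4 to 9 points.

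**(iii) Correlation that decays with time, plus measurement noise.** The variance is split into a stable part p, a part q whose correlation over 12 weeks is a, and noise e.

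| p, q, e, a | Week 0 only | With earlier mean |
|---|---|---|
| 0.5, 0.4, 0.1, 0.3 | 79.3% | 81.7% |
| 0.5, 0.3, 0.2, 0.3 | 80.1% | 83.7% |
| 0.3, 0.65, 0.05, 0.5 | 79.2% | 79.8% |
| 0, 0.85, 0.15, 0.7 | 79.9% | 81.2% |
| 0, 0.95, 0.05, 0.5 | 82.9% | 83.0% |

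These gains run from under 0.1 to 3.6 points. More noise or less decay moves the result towards case (i), so I allow 0 to about 5. Applying the eligibility limits to the first two rows gives 78.4% to 80.3% and 80.2% to 83.0%.

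**(iv) First-order decay with no measurement error.** Week 0 carries all the information, so the residual SD does not change. The lost degree of freedom costs about 0.01 point of power.

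**The case against.** The strongest reply is that nothing is broken. Adjusting change for the baseline that defines it is standard and valid. Protocol and SAP agree, and neither the type I error nor the quantity estimated is in doubt. That stands in full.

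The size can also be challenged. Equal correlation of 0.8 with an SD of change of 0.80 implies a between-subject HbA1c SD of 0.80/√0.4 = 1.26, whereas even a uniform spread over 7.0% to 10.0% has SD 3/√12 = 0.87. Equal correlation also treats readings 6 and 12 weeks apart as equally related, which favours the earlier values. So the 12-point figure is an upper limit and not an expectation.

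Two stronger readings are tempting, and the documents support neither:

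- A reader might infer that the primary analysis has 70.6% power and that the omitted values would lift it from there. The 70.6% belongs to the unadjusted t-test; the planned ANCOVA already does better under any correlation in the table. It also rests on an SD of 0.80%, above the 0.523% to 0.628% that the protocol reports from Study CCT-002 (a different population, JDS scale).
- A reader might infer that the plan rules the earlier values out. The supplementary ANCOVA in protocol 13.1.3 could include them. It does not name them, however, and it is not the primary analysis, so the point is only partly answered.

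**Conclusion.** The point holds as an efficiency improvement. The primary model leaves out two pre-randomisation measurements of its own outcome, and no other provision brings them into the primary comparison. Because they precede randomisation, adjusting for them introduces no bias and changes neither endpoint nor treatment effect.

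The gain depends on correlations that the documents do not report. At a true difference of -0.40%, SD of change 0.80% and 51 per group, the most realistic range is a few percentage points, with 8 to 9 as the ceiling once eligibility is taken into account. The possible loss is negligible, which is why the change is worth making although its benefit cannot be fixed in advance. A claim that the planned analysis is invalid, or that the change would restore the 90% power first planned, would go beyond the documents.

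**What to change.** Before unblinding, amend SAP 2.1.1, protocol 13.1.3 and the protocol summary so that the primary ANCOVA contains treatment group, Week 0 HbA1c, and the mean of the Week -6 and Week -2 HbA1c as a second continuous covariate. Where one of the two is missing, use the available one; otherwise the missing-data rule in SAP 2.4.2 could drop the subject. Align SAP 2.4.1, and keep the Week 0-only model as a supportive analysis.

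Week 0 should stay in the model. Replacing it with the mean of all three readings can lose precision: under error-free decay with a 12-week correlation of 0.7, power falls from 77.4% to 74.6%.

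A pooled, blinded estimate of the between-visit correlations would show the likely gain, if a figure is wanted. The cost is one model term, a line of text in each place and one degree of freedom. No new patients, visits or samples are needed.
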